7.2 NULL AND ALTERNATIVE HYPOTHESES

No formal hypothesis testing is planned in this trial. All analyses in this trial are descriptive and exploratory by nature.

7.3 PLANNED ANALYSES

Only one analysis population will be considered for efficacy and safety analyses: the treated set. The treated set (TS) will consist of all patients who were treated with at least one single dose of BI 836880.

The primary analysis will be based on the treated set population excluding patients that have to be replaced for analysis of the MTD, see [section 3.3.4.1](#) for further details.

No per protocol population will be used for analyses; however protocol violations will be identified and listed.

[figure not shown]
7.3.1 Primary endpoint analyses

In order to determine the MTD the occurrence of a DLT in the first cycle will be assessed on an individual patient level. The MTD will be determined as described in [section 7.1](#).

Based on the data observed in the trial other models might be considered either additionally or replacing the primary model. For feasibility or other reasons a different dose might be considered as the recommended dose for Phase II.

7.3.2 Secondary endpoint analyses

Please refer to [section 7.3.4](#) for safety related secondary endpoints and [section 7.3.5](#) for PK related endpoints.

7.3.4 Safety analyses

All patients of the treated set will be included in the safety analyses. Two analyses will be performed. The first analysis of safety will be performed for the first part of the trial

(determination of the MTD, first cycle only, treatment regimen = initial dose at the start of the treatment, treated set). This descriptive analysis will evaluate the MTD for the monotherapy of BI 836880. The second analysis will be performed with respect to all cycles and will act as a support for the determination of the MTD (treated set).

Events that started between the first administration of the treatment until 6 weeks (42 days) after the last administration of treatment will be considered as having occurred on treatment. In general, later events will be attributed to the post-study period and will be presented separately. However, post-study events will be examined to determine whether they need to be combined with on-treatment events in an additional table.

Adverse events will be graded according to CTCAE Version 4.03 ([R12-2532](#)) and reported according to BI standards. *Frequency, severity, and causal relationship of adverse events will be tabulated by system organ class and preferred term after coding according to the current version of the Medical Dictionary for Drug Regulatory Activities (MedDRA).*

Serious adverse events will be tabulated. In addition, events leading to dose reduction or treatment discontinuation will be examined, but may not be reported as individual tables, depending upon the extent of overlap. Descriptive statistics will be used to describe changes in laboratory tests over time. In addition, all abnormalities of potential clinical significance will be reported. In general, potential clinical significance is defined as at least CTCAE Grade 2 and an increase in CTCAE classification from baseline. The incidence and intensity of the more important adverse events (as determined from the analyses above) will be correlated descriptively with pharmacokinetic data, if possible.

Adverse events will be coded using the Medical Dictionary for Regulatory Activities (MedDRA) coding dictionary. Standard BI summary tables and listings will be produced. All adverse events with an onset between start of treatment and end of the residual effect period (REP), a period of 42 days after the last dose of trial medication, will be assigned to the treatment period for evaluation.

All treated patients will be included in the safety analysis. In general, safety analyses will be descriptive in nature and will be based on BI standards. No hypothesis testing is planned.

Adverse events that start before first drug intake and deteriorate under treatment will also be considered as 'treatment-emergent'.

Laboratory data will be analysed both quantitatively as well as qualitatively. The latter will be done via comparison of laboratory data to their reference ranges. Values outside the reference range as well as values defined as clinically relevant will be highlighted in the listings. Treatment groups will be compared descriptively with regard to distribution parameters as well as with regard to frequency and percentage of patients with abnormal values or clinically relevant abnormal values.

Vital signs, physical examinations, or other safety-relevant data observed at screening, baseline, during the course of the trial and at the end-of-trial evaluation will be assessed with regard to possible changes compared to findings before start of treatment.

7.3.5 Pharmacokinetic analyses

Refer to [section 5.4.1](#) for pharmacokinetic parameters to be calculated using non-compartmental analysis (NCA).

All evaluable subjects who received at least one dose of BI 836880 will be included in the pharmacokinetic analysis. Subjects who are considered as not evaluable will be listed with their individual plasma concentrations and individual pharmacokinetic parameters, however, will not be included in descriptive statistics for plasma concentrations, pharmacokinetic parameters or other statistical assessment.

Every effort will be made to include all concentration data in an analysis. If not possible, a case to case decision is required whether the value should only be excluded from half-life estimation or the complete analysis.

- If a concentration is only excluded from half-life determination, it will be used for all other calculations (e.g. descriptive statistics) and for graphical presentation.
- If a concentration value is excluded from all calculations, it will not be presented graphically or used for the calculation of descriptive statistics and parameter determination. However the excluded concentration itself will be listed in the clinical trial report associated with an appropriate flag.

[figure not shown]
Concentrations will be used for graphs and calculations in the format that is reported in the bioanalytical report. Noncompartmental pharmacokinetic analyses of the plasma concentration-time data will be performed using a validated software program, e.g. Phoenix WinNonlin. Only concentrations within the validated concentration range will be used for the calculation of pharmacokinetic parameters. For pre-dose samples, the actual sampling time will be set to zero.

[figure not shown]
Plasma concentrations will be plotted graphically versus time for all evaluable subjects as listed in the drug plasma concentration-time tables. For the presentation of the mean profiles, the geometric and arithmetic mean and the planned blood sampling times will be used. If the actual sampling time deviates significantly from the planned time, the corresponding plasma concentration will be excluded from the calculation of descriptive statistics.

The following descriptive statistics will be calculated for analyte concentrations as well as for all pharmacokinetic parameters: N, arithmetic mean, standard deviation, minimum, median, maximum, P10, Q1, Q3, P90, arithmetic coefficient of variation, geometric mean, and geometric coefficient of variation. The data format for descriptive statistics of concentrations will be identical with the data format of the respective concentrations. The descriptive statistics of pharmacokinetic parameters will be calculated using the individual values with the number of decimal places as provided by the evaluation program. Then the individual

Proprietary confidential information © 2019 Boehringer Ingelheim International GmbH or one or more of its affiliated companies

values as well as the descriptive statistics will be reported with three significant digits in the clinical trial report.

7.4 INTERIM ANALYSES

Interim safety evaluations will be performed as considered necessary. In particular safety evaluations will be performed after each dose cohort by the DSB consisting of the investigators and representatives of the sponsor (refer to [section 3.1.1](#)). Based on this the DSB will recommend the next dose level as well as the corresponding cohort size. DSB meeting minutes and outputs provided for these DSB meetings will be documented and archived in the clinical trial master file (CTMF).

If considered necessary, as soon as the MTD is determined an evaluation of the safety aspects will be performed. Results of this evaluation will be documented and archived. If applicable such an analysis will be defined in more detail in the TSAP.

7.5 HANDLING OF MISSING DATA

No imputation will be performed on missing efficacy data.

Missing baseline laboratory values will be imputed by the respective values from the screening visit. No other imputations will be performed on missing data although every effort will be made to obtain complete information on all adverse events and to follow-up the patients for efficacy data.

Pharmacokinetics:

Drug concentration-time profiles: Concentration data identified with NOS (no sample), NOR (no valid result), NOA (not analyzed), BLQ (below the limit of quantification) and NOP (no peak detectable) will be ignored and not replaced by zero at any time point (including the lag phase). Descriptive statistics of concentrations at specific time points will be calculated only when at least 2/3 of the individuals have concentrations within the validated concentration range.

Pharmacokinetic parameters: In the non-compartmental analysis, concentration data identified with NOS, NOR and NOA will not be considered. BLQ and NOP values in the lag phase will be set to zero. The lag phase is defined as the period between time 0 and the first time point with a concentration above the quantification limit. All other BLQ and NOP values of the profile will be ignored. Descriptive statistics of parameters will be calculated only when at least 2/3 of the individual parameter estimates of a certain parameter are available. Pharmacokinetic parameters which cannot be determined will be identified by "not calculated" (NC).

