CLINICAL TRIAL PROTOCOL

Document Number:		c02441868-07
EudraCT No.:	2014-005395-28	
BI Trial No.:	1336.1	
BI Investigational Product(s):	BI 836880	
Title:	A First-in Human Phase I, non-randomized, open-label, multi-center dose escalation trial of BI 836880 administered by repeated intravenous infusions in patients with solid tumors.	
Brief Title:	Dose finding study of BI836880 in patients with solid tumors	
Clinical Phase:	Phase I	
Trial Clinical Monitor:	[REDACTED] Phone: [REDACTED] Fax: [REDACTED]	
Coordinating Investigator:	[REDACTED] Phone: [REDACTED] Fax: [REDACTED]	
Status:	Final Protocol (revised protocol based on global amendment 5)	
Version and Date:	Version:	Date:
	6.0	08 March 2019
Page 1 of 103		
Proprietary confidential information. © 2019 Boehringer Ingelheim International GmbH or one or more of its affiliated companies. All rights reserved. This document may not - in full or in part - be passed on, reproduced, published or otherwise used without prior written permission.		

CLINICAL TRIAL PROTOCOL SYNOPSIS

Name of company:	Boehringer Ingelheim		
Name of finished product:	not applicable		
Name of active ingredient:	BI 836880		
Protocol date: 11 May 2015	Trial number: 1336.1		Revision date: 08 March2019
Title of trial:	A First-in Human Phase I, non-randomized, open-label, multi-center dose escalation trial of BI 836880 administered by repeated intravenous infusions in patients with solid tumors.		
Coordinating Investigator			
Trial site(s):	Multi-centre trial conducted in 2 countries		
Clinical phase:	Phase I; First In Human		
Objective(s):	Objective of this trial is to determine the maximum tolerated dose (MTD) of BI 836880 and to provide preliminary safety data given as intravenous infusion and to determine recommended phase II dose. Further the PK-, immunogenicity and PD-profile, as well as primary signs of anti-tumor activity of BI 836880 should be assessed.		
Methodology:	Non-randomized, uncontrolled, open-label, dose escalating study of BI 836880 administered intravenously		
No. of patients:	About 80 patients will be entered, including at least 12 patients treated at MTD with tumour lesions evaluable for Dynamic contrast-enhanced (DCE)-MRI.		
total entered:	80		
each treatment:	80 (all patients will receive trial drug, but on different dose levels)		

Name of company:	Boehringer Ingelheim	
Name of finished product:	not applicable	
Name of active ingredient:	BI 836880	

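### In the concentration-time summaries, values below quantification are treated like missing samples, so any summary printed at a time point where they occur is biased upward

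*Protocol*

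**What the plan says.** Protocol section 7.5, under Pharmacokinetics, gives two sets of rules.

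- **Concentration-time profiles.** Five codes share one rule: no sample (NOS), no valid result (NOR), not analysed (NOA), BLQ and NOP. All "will be ignored and not replaced by zero at any time point (including the lag phase". Descriptive statistics at a time point are "calculated only when at least 2/3 of the individuals have concentrations within the validated concentration range".
- **Pharmacokinetic parameters (non-compartmental analysis, NCA).** Here the codes are separated. NOS, NOR and NOA are not considered. For the other two, "BLQ and NOP values in the lag phase will be set to zero", and "All other BLQ and NOP values of the profile will be ignored".

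Section 7.3.5 lists the statistics: "N, arithmetic mean, standard deviation, minimum, median, maximum, P10, Q1, Q3, P90", followed by the arithmetic CV, geometric mean and geometric CV. It also plots mean profiles from the geometric and arithmetic means. For individual data it states: "Plasma concentrations will be plotted graphically versus time for all evaluable subjects as listed in the drug plasma concentration-time tables".

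SAP section 6.6 refers missing PK data to an internal standard and back to protocol 7.5. Its visible text adds no count of BLQ values.

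**The concern.** NOS, NOR and NOA mean that nothing usable is known about the concentration. BLQ means that it lies below every quantified value at that time point. Setting both aside discards the low end of the distribution, so every location statistic computed from the remainder can only stay the same or rise. If a patient's trough falls from low to unquantifiable, the printed mean trough goes up. The NCA paragraph of the same section recognises the difference between the two kinds of code; the concentration paragraph does not.

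This has some bearing on the trial's questions. Section 4.1.3 explains the dose range by troughs expected to exceed a targeted minimum concentration. Pre-dose samples are planned through course 12 (Appendix 10.4), and section 3.1 has the recommended phase II dose confirmed on all safety, PK and pharmacodynamic data. The synopsis also names immunogenicity among the profiles to be assessed ("Further the PK-, immunogenicity and PD-profile"). Loss of measurable drug in some patients is something a reader would look for in a table of troughs by visit.

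**Working it through.** The plan gives no figure to reproduce: no lower limit of quantification (LLOQ), no variability, no trough level and no BLQ rate. The sizes below therefore rest on stated assumptions.

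**1. How many BLQ values can be dropped while a summary is still printed.** From the two-thirds rule, the maximum is n − ceil(2n/3), reached only if no sample is missing for another reason.

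| n | quantifiable values needed | most BLQ dropped |
|---|---|---|
| 2 | 2 | 0 |
| 3 | 2 | 1 |
| 4 | 3 | 1 |
| 6 | 4 | 2 |
| 12 | 8 | 4 |

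Two is the minimum cohort size and 12 the planned upper size of the group at the MTD (section 3.1).

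**2. BLQ as the lower tail of one lognormal.** Let s = √ln(1 + CV²) and f = the share BLQ. Relative to the true values, the statistics on quantifiable values are:

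- geometric mean ratio = exp[s·φ(z_f)/(1 − f)]
- median ratio = exp[s·Φ⁻¹(f + (1 − f)/2)]

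At the cap, f = 1/3, z_f = −0.431, φ(z_f) = 0.364, φ/(1 − f) = 0.545 and Φ⁻¹(2/3) = 0.431.

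| Assumed CV | s | geometric mean ratio | median ratio |
|---|---|---|---|
| 30% | 0.294 | 1.17 | 1.13 |
| 50% | 0.472 | 1.29 | 1.23 |
| 80% | 0.703 | 1.47 | 1.35 |

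At 50% CV with smaller shares, the geometric mean and median ratios are 1.22 and 1.16 for f = 1/4, and 1.15 and 1.10 for f = 1/6.

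**3. BLQ patients have truly lost the drug.** This is a different model: a share f at about zero and the rest lognormal. The arithmetic mean ratio against BLQ = 0 is 1/(1 − f): 1.05 at 5%, 1.11 at 10%, 1.25 at 20% and 1.50 at one third. The median ratio is 1/exp[s·Φ⁻¹((0.5 − f)/(1 − f))]. At one third it is 1.22 for 30% CV, 1.38 for 50% and 1.75 for 100%.

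**4. A small example with assumed values.** Six troughs of 0, 0, 60, 80, 100 and 120 have mean 360/6 = 60 and median 70. With the two zeros dropped, the mean is 360/4 = 90, the median 90 and the minimum 60.

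**5. How often this would happen.** Suppose each patient has a 20% chance of being BLQ and no samples are missing. The chance that a summary is printed with at least one BLQ patient left out is P(1 ≤ X ≤ k), with X ~ Bin(n, 0.2) and k from step 1. It is 0.38 for n = 3, 0.64 for n = 6 and 0.86 for n = 12. The summary is suppressed with probability 0.10, 0.10 and 0.07.

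**The case against.** The case for leaving the rule alone has several sound parts.

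- **BLQ may not occur at the doses that matter.** The molecule has an albumin-binding half-life extension (section 1.2), and the modelling in section 4.1.3 expects steady-state troughs above target at 360 and 720 mg. If so, the bias there is zero. This stands, and the point is conditional for that reason.
- **The two-thirds rule limits the damage.** It caps the loss at one third, excludes it in a two-patient cohort and suppresses the summary beyond the cap. It also covers absences of every kind, so the one-third figure is reached only when all of them are BLQ.
- **Nobody is hidden.** A reader might infer that patients who lose exposure vanish from the report. N is printed, and concentrations are listed and plotted for all evaluable patients. What remains is narrower: N alone cannot separate a BLQ result from a missed sample.
- **No named endpoint is touched.** A reader might infer that the trial's exposure endpoint is overstated. The PK secondary endpoints are first-dose AUC0-tz and half-life, which follow the NCA rules. The visible text names no trough endpoint, and the PK interim for the Data Safety Board (section 5.4.1) names Cmax, AUC and half-life as possible parameters.
- **Some PK text is redacted, and the SAP relies on internal standards.** These may already flag BLQ values, so no claim is made that such a flag is absent from the sponsor's outputs.

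None of this changes what section 7.5 instructs when a BLQ value does occur: the low result is set aside and the statistics are computed on the rest.

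**Conclusion.** The point holds as a conditional and minor one. Following section 7.5 as written, any time point with BLQ values and a printed summary gives a median, minimum, lower percentiles and means for patients with measurable drug only, and these are biased upward for the whole group. At the one-third cap, the lower-tail model gives a median 13–35% and a geometric mean 17–47% too high for CVs of 30–80%. The drug-loss model gives an arithmetic mean up to 1.5-fold too high. The two models answer different questions, so the lower-tail percentages should not be read as the size of a drug-loss effect. Both rest on an assumed BLQ share and spread, and with no BLQ the error is nil.

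The documents do not support reading this as a flaw in the primary analysis, in the AUC0-tz or half-life endpoints, or in the dose recommendation. All analyses are declared descriptive and exploratory (section 7.2). It is a display weakness that is cheap to remove.

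**What to change.** In protocol 7.5, for the concentration summaries only, separate BLQ and NOP from NOS, NOR and NOA, as the NCA paragraph already does. Carry this into the SAP. Then:

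1. At each time point, print the number BLQ and the number missing beside N.
2. Compute the median, quartiles, P10 and minimum with BLQ ranked as the lowest values, printing `<LLOQ` where a quantile falls among them. No value is imputed.
3. Keep the two-thirds rule for the arithmetic and geometric means, and label them 'quantifiable values only' wherever any BLQ occurs, including on the mean-profile figure.

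Step 3 leaves the means numerically unchanged; the label and the BLQ count tell the reader what they cover. State explicitly that the two-thirds rule then governs the means, since ranked quantiles stay interpretable at higher BLQ shares.

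The cost is a small programming change to the concentration table and mean-profile figure, and a departure from the sponsor's default display. The NCA rules are unchanged and no new data are needed.

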7.6 RANDOMISATION

Patients will be assigned, not randomised, into escalating dosage cohorts by order of admission into the trial. Doses will be assigned based on the decision made by the DSB (see [section 7.4.](#)).

7.7 DETERMINATION OF SAMPLE SIZE

About 40 patients will be expected for the dose finding part and confirmation of RP2D. Fewer patients might be needed based on the recommendation of the DSB and the criteria specified (see [section 7.1](#)). Additional 40 patients will be included in the expansion cohorts, in case two (or three) tumor types will be selected for further evaluation.

8. INFORMED CONSENT, DATA PROTECTION, TRIAL RECORDS

The trial will be carried out in compliance with the protocol, the principles laid down in the Declaration of Helsinki, in accordance with the ICH Harmonised Tripartite Guideline for Good Clinical Practice (GCP) and relevant BI Standard Operating Procedures (SOPs). Standard medical care (prophylactic, diagnostic and therapeutic procedures) remains in the responsibility of the treating physician of the patient.

The investigator should inform the sponsor immediately of any urgent safety measures taken to protect the study subjects against any immediate hazard, and also of any serious breaches of the protocol/ICH GCP.

The rights of the investigator and of the sponsor with regard to publication of the results of this trial are described in the investigator contract. As a rule, no trial results should be published prior to finalization of the Clinical Trial Report unless there is public interest to publish before the end of the trial. In this event the Sponsor and the investigator(s) will agree on the publication strategy

Insurance Cover: The terms and conditions of the insurance cover are made available to the investigator and the patients via documentation in the ISF (Investigator Site File).

The trial will be carried out in compliance with the protocol, the ethical principles laid down in the Declaration of Helsinki, in accordance with the ICH Harmonized Tripartite Guideline for Good Clinical Practice (GCP) and relevant BI Standard Operating Procedures (SOPs).

Standard medical care (prophylactic, diagnostic and therapeutic procedures) remains in the responsibility of the treating physician of the patient.

The Investigator will inform the Sponsor immediately of any urgent safety measures taken to protect the trial subjects against any immediate hazard, and also of any serious breaches of the protocol or of ICH GCP.

The certificate of insurance cover is made available to the Investigator and the patients, and is stored in the ISF (Investigator Site File)."

8.1 TRIAL APPROVAL, PATIENT INFORMATION, AND INFORMED CONSENT

This trial will be initiated only after all required legal documentation has been reviewed and approved by the respective Institutional Review Board (IRB) / Independent Ethics Committee (IEC) and competent authority (CA) according to national and international regulations. The same applies for the implementation of changes introduced by amendments.

Prior to patient participation in the trial, written informed consent must be obtained from each patient according to ICH GCP and to the regulatory and legal requirements of the

participating country. Each signature must be personally dated by each signatory and the informed consent and any additional patient-information form retained by the investigator as part of the trial records. A signed copy of the informed consent and any additional patient information must be given to each patient or the patient's legally accepted representative.

The patient must be informed that his/her personal trial-related data will be used by Boehringer Ingelheim in accordance with the local data protection law. The level of disclosure must also be explained to the patient.

The patient must be informed that his / her medical records may be examined by authorised monitors (CML/CRA) or Clinical Quality Assurance auditors appointed by Boehringer Ingelheim, by appropriate *IRB / IEC* members, and by inspectors from regulatory authorities.

